Optimising the Management of Patients with Heart Failure with Preserved Ejection Fraction in Primary Care

Work Package 1

Protocol:

Management of Patients with Heart Failure with Preserved Ejection Fraction: What do Patients and Providers Need and Want?

Contents

2.0 Plain English Summary.....	4
2.1 Background and Rationale	54
2.3 Hypothesis and Aims	65
3.0 Abstract.....	65
4.0 Objectives.....	6
5.0 Methods.....	6
6.0 Patient Sample.....	76
7.0 Inclusion Criteria Patients	7
8.0 Exclusion Criteria Patients.....	87
9.0 Healthcare Provider Sample.....	87
10.0 Data collection.....	87
11.0 Analysis	8
12.0 Outcomes/Outputs.....	98
13.0 Research Sites and Research Process.....	109
14.0 Project timetable	1110
15.0 References.....	1312

Trial Title	Management of Patients with Heart Failure with Preserved Ejection Fraction: What do Patients and Providers Need and Want?
Short Title	HFpEF (Qualitative) Patients & Providers
Trial Design	Qualitative study using semi-structured interviews and framework analysis.
Trial Participants	Patients with Heart Failure with Preserved Ejection Fraction (HFpEF), health care providers (HCP) from primary care and specialist services, and commissioners.
Planned Sample Size	Approximately 50 patients, and 50 providers and commissioners
Follow-up Duration	No follow up required
Planned Trial Period	27 months: January 2018 to May 2020.
Objectives	
We hypothesise that outcomes of patients with HFpEF can be improved through optimising their management and self-management, and increasing coordination between primary care and specialist services. We believe that patients and healthcare providers will have useful ideas and perspectives on management and self-management of HFpEF, and how it can be supported.
 
Specific Objectives:
 
 1) Explore patients' understanding of and perspectives on HFpEF and comorbidities; 2) Describe patient strategies for monitoring and managing symptoms, medications, exercise and diet; 3) Determine patient preferences related to care and support needed; 4) Explore providers' (GPs, practice nurses and Heart Failure (HF) Specialists) and commissioners' understanding of and perspectives on managing HFpEF and comorbidities, organisation of care, the type of support feasible to provide in primary care, and collaboration between primary and specialist services. 
Amendment: The aim of this proposal is to determine clinical management strategies for patients with HF and HFpEF by primary care and specialist providers during and after the pandemic. The specific research questions are:
 
 1. How are patients with HF and HFpEF being managed (telephone consultation, video-conferencing, home visits, clinic visits, postponement) during the pandemic crisis and lockdown? 2. How effective do providers and patients think non face-to-face methods of consultation and current strategies are for patients with HF and HFpEF? 3. What are the expected consequences of the pandemic on management of people with long-term conditions such as HF and HFpEF? 4. What are potential changes to practice (primary care, specialist services) as a result of the COVID-19 pandemic? 5. What methods and strategies are planned and/or needed for managing patients with HF and HFpEF once health care provision returns to 'normal'?

	6. How could health care services be re-designed to ensure greater flexibility to meet the challenges of catastrophic events such as this pandemic?	
Funder	National Institute for Health Research/National School for Primary Care Research (NHIR SPCR) Grant ref no: 347	
Sponsor	Cambridge University Hospital NHSFT and the University of Cambridge	
Chief Investigator	[name] Florence Nightingale Professor of Clinical Nursing Research University of Cambridge	
Co-Investigators	Cambridge	[name]
		[name]

2.0 Plain English Summary

Heart failure (HF) is a condition in which the heart does not work well to pump blood around the body. About half of patients with HF have a type of HF in which the heart is very stiff, which is more common in older people with a history of high blood pressure, obesity and diabetes. It is harder to diagnose and is less well recognised and understood. No specific drugs have been found to help this type of HF, except for diuretics or 'water pills'. Controlling blood pressure and blood sugar, and being active are recommended for patients with this HF. Most patients are managed in primary care sometimes in collaboration with specialists. In this study we want to ask patients with this type of HF about their challenges, how they manage HF and their other conditions, and ask patients, primary care providers, HF nurses and doctors, and commissioners about what they think will improve management and how to organise care. We will recruit and obtain consent from approximately 50 patients from a wide range of backgrounds and 50 healthcare providers from primary care and HF specialist services to talk to us. At times patients' carers may wish to provide information and contribute to the interview. When this happens, with their consent, we will note their comments and include these in the study. Interviews can be by telephone or in a place of the person's choosing, and will be audio-recorded and transcribed. It is confidential: no identifying information will be on the interviews or written transcripts so no one will know who it is. We will use what people tell us to improve the management of this type of HF: to help patients manage symptoms and have better quality of life, and to make sure that patients get the right care. We will talk to patient groups and providers about what people have told us, and use the information as part of a programme of research to improve management.

2.1 Background and Rationale

Approximately half of patients with HF will have a preserved ejection fraction (HFpEF) rather than a reduced ejection fraction (HFrEF), especially among older patients (1,2). HFpEF is less well understood and less easily diagnosed than HFrEF, and often not identified in primary care (3). Patients are usually older with multiple comorbid conditions such as obesity, hypertension and diabetes, and more likely to be women (4). HFpEF has been labelled a 'stealth syndrome', and better understanding and treatment called an urgent priority (5). HFpEF greatly affects patient well-being: patients with HFpEF reported greater consequences of HF on their lives, more symptoms and the same or worse quality of life than those with HFrEF (6,7). Epidemiological trends in the US has shown hospitalisations for HFpEF increasing, while those for HFrEF were decreasing; however both groups experienced readmission rates of 29% in 60-90 days (8). In-hospital mortality for HFpEF in studies was 2.5-6.5%, with 6 month mortality rates of 14-16%, similar to HFrEF (9).

Unlike HFrEF, HF specific pharmacological therapy (ACE inhibitors, beta blockers) has not been shown to improve morbidity and mortality in HFpEF (10). Thus age, comorbidity and lack of evidence-based treatment in an under-recognised type of HF pose a challenge for improving outcomes. However, others argue that management of comorbidities is key to managing HFpEF given that these conditions are thought to drive the development of HFpEF through promotion of inflammation (11,12). Class I recommendations in the latest European guidelines are to manage comorbidities and use diuretics to manage fluid status as needed (10). Providers and patients may be uncertain about what can be done to manage HFpEF, or to better organise care. Previous studies in HF have shown challenges in diagnosis, provider knowledge, and in organisation of services with fragmentation and discontinuity being common (3,13). Self-management in HFpEF is little explored. Similar to HFrEF patients with HFpEF will need to monitor fluid retention, blood pressure and potentially blood glucose, whilst managing symptoms, medications, diet and physical activity.

Most studies of self-management in HF have focused on patients with HFrEF and the HF alone rather than HFpEF plus comorbidities. Studies of HF self-management that have reported including both HFrEF and HFpEF did not provide specific information regarding patients with HFpEF, or proportion in the sample (14), and in one study the mean age (57 ± 13) and mean ejection fraction (28.4 ± 12) made it unlikely that there were many patients with HFpEF (15). Patients with either HFpEF or HFrEF are likely to face similar challenges in self-management, and need pro-active support and timely communication with familiar providers (14). Given the uncertainty and lack of evidence for management and self-management of this patient group, it is important to determine what patients and providers are currently doing and what they wish for in terms of

management and support. The purpose of this study is to explore primary care providers', HFSNs' and patients' perspectives on management and self-management of HFpEF and comorbid conditions, the type of support needed and what is feasible to provide optimal management.

2.3 Hypothesis and Aims

We hypothesise that outcomes of patients with HFpEF can be improved through optimising their management and self-management, and increasing coordination between primary care and specialist services. We believe that patients and providers will have useful ideas and perspectives on management and self-management of HFpEF, and how it can be supported.

3.0 Abstract

Approximately half of patients with heart failure (HF) have heart failure with preserved ejection fraction (HFpEF), and are usually older with multiple comorbid conditions. HF-specific medications used in HF with reduced EF have not been found to reduce mortality and morbidity in HFpEF, but management of comorbidities is essential as these contribute to development and progression of HFpEF. Providers and patients may be uncertain about what can be done to manage HFpEF. The purpose of this study is to explore patients' and providers' perspectives on management, self-management, support needed and its feasibility.

4.0 Objectives

- 1) Explore a variety of patients' (including those from Black and minority ethnic groups) understanding and perspectives of HFpEF and comorbidities
- 2) Describe patient strategies for monitoring and managing symptoms, medications, exercise and diet
- 3) Determine patient preferences for care
- 4) Explore healthcare providers' understanding of and perspectives on managing HFpEF and comorbidities, organisation of care and type of support feasible

5.0 Methods

Qualitative study employing semi-structured interviews with patients and healthcare professionals. Patients may be supported by an informal carer for the interview.

6.0 Patient Sample

Approximately 50 patients with HFpEF; and approximately 50 health care providers to include general practitioners, practice nurses, heart failure specialist nurses, cardiology consultants to be recruited from 3 regions in UK (Cambridgeshire, Greater Manchester, Northwest Coast & West Midlands). Patients: Around 50 patients identified with HFpEF across the above 3 regions in England. This number of participants may increase if there are new themes arising from interviews as the intent will be to reach data saturation. We will recruit patients from practices both rural and urban, and will work to include fairly equal numbers of women and men, and a variety of comorbid conditions. Our current investigation indicates that 40% of patients on HF registers can be identified as HFpEF or probable HFpEF.

We will invite patient participants initially from a purposive sample of practices through the Cambridgeshire and Peterborough clinical commissioning group (CCG), and the primary care clinical research network in the East of England, including those referred to specialist services in Cambridgeshire and Peterborough. Estimating a 50% recruitment rate, we would need 3-4 practices with HF registers of 50-100 patients to recruit our initial sample. We will then add additional sites in the North of England to our study; specifically secondary care centres and primary care practices located in the CRNs of Greater Manchester, Northwest Coast and West Midlands. The sites will purposively recruit patients to ensure additional participation from black and minority ethnic groups (BME), different ages and comorbidities, and providers and commissioners working within different systems and CCGs. Adding these sites will develop our understanding iteratively and enable us to determine commonalities and differences in diverse patients e.g. ethnicities, providers and regional health care systems.

7.0 Inclusion Criteria Patients

Adult patients with:

- Diagnosis of diastolic dysfunction or HFpEF

OR

- Diagnosed with HF and a reported 'normal' EF or EF \geq 50%

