13.0 Research Sites and Research Process

Cambridge: Cambridge University Hospitals (CUH) NHS Foundation Trust; Manchester: Manchester University NHS Foundation Trust (MFT) which covers Central Manchester University Hospitals NHS Foundation Trust (CMFT) and University Hospital of South Manchester NHS Foundation Trust (UHSM); Northern Care Alliance NHS Group which covers Salford Royal NHS Foundation Trust and The Pennine Acute Hospitals NHS Trust. Keele: University Hospitals of North Midlands, which includes Royal Stoke Hospital and County Hospital).

Practices will review patients on the HF register using the inclusion and exclusion criteria and send eligible patients a cover letter, patient information sheet, informed consent and expression of interest. Patients will be able to return the expression of interest by pre-paid post, or ring the study administrator or research nurse. In a previous qualitative study of patients with HFREF, we found that this was a reasonable approach for recruiting patients. We will also ask the practices to talk to eligible patients attending clinic visits, and determine if they are willing to be approached about the study. Patients will be offered as much time as its needed to consider participation. Interested patients will be contacted by the SRA / RA or research nurse to explain the study, answer questions and go through the informed consent form. Consent may be taken at time of face-to-face interview or mailed via pre-paid post if the interview is by telephone. Verbal consent will also be confirmed at time of interview.

Interviews will be conducted at a place of the patient's choosing or via telephone. The same procedures and semi-structured interview guide will be used in all sites. Patient invitations will be issued from the recruiting service (using their headed paper). Interviews will be semi-structured to allow for additional questions (arising from earlier interviews), probing of answers and a relaxed conversational style. We will audio-record the interviews with permission and transcribe them verbatim. These data may be complemented by additional comments made by the patient's carer if they are present at the interview and are willing to provide written informed consent for their data to be included to add context to the study. Patient (and carer if present) identifying information will not be recorded or appear on the transcripts.

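### Entry on diastolic dysfunction carries no ejection-fraction condition, so a heart failure patient with a recorded EF below 50% can qualify for a sample described as HFpEF

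*Protocol*

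**What the plan says.** The protocol synopsis gives the trial participants as "Patients with Heart Failure with Preserved Ejection Fraction (HFpEF), health care providers (HCP) from primary care and specialist services, and commissioners". Section 6.0 likewise describes about 50 patients identified with HFpEF.

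Section 7.0 admits adults by either of two routes joined by OR:

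- Route 1: "Diagnosis of diastolic dysfunction or HFpEF".
- Route 2: "Diagnosed with HF and a reported 'normal' EF" or an EF of at least 50%.

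The exclusions in section 8.0 are cognitive impairment, not speaking English, and end-of-life care or another life-threatening condition. None concerns EF or the absence of HF.

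On recruitment, section 13.0 states: "Practices will review patients on the HF register using the inclusion and exclusion criteria". It adds a second practice route: "We will also ask the practices to talk to eligible patients attending clinic visits". Section 6.0 says the practice sample is drawn "including those referred to specialist services in Cambridgeshire and Peterborough", and that later sites are "specifically secondary care centres and primary care practices located in the CRNs of Greater Manchester", Northwest Coast and West Midlands. It also puts the share of HF-register patients identifiable as HFpEF or probable HFpEF at 40%.

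**The concern.** The two routes are not equally strict. Route 2 ties entry to both HF and preserved EF. Route 1, when met through diastolic dysfunction, ties it to neither. The eligibility rule is therefore wider than the population it is meant to select.

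This matters because of the study's own rationale. Section 2.1 faults earlier self-management studies for including both types of HF without giving HFpEF-specific information or the proportion in the sample. If some patients here have reduced EF and nobody records which, accounts of symptoms, self-management and preferences from those patients could be reported as HFpEF needs. They would then feed the HFpEF management programme that section 11.0 says the findings will inform. Section 11.0 describes no charting by diagnostic basis, so a reader of the results could not tell.

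**Working it through.** No sample-size, power or error-rate figure is involved, so the check is one of logic. Each patient profile is run through section 7.0 and then through the register screen in section 13.0.

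| Profile | Section 7.0 wording | After HF-register screen | Fits HFpEF target? |
|---|---|---|---|
| A. Labelled HFpEF | Eligible (route 1) | Eligible | Yes |
| B. HF, normal EF or EF at least 50% | Eligible (route 2) | Eligible | Yes |
| C. HF, diastolic dysfunction, no EF reported | Eligible (route 1) | Eligible | Plausibly, as probable HFpEF |
| D. HF, diastolic dysfunction, EF recorded below 50% | Eligible (route 1) | Eligible | No |
| E. Diastolic dysfunction, no HF | Eligible (route 1) | Removed where the register is used | No |
| F. HF, EF below 50%, no diastolic dysfunction or HFpEF label | Not eligible | Not eligible | No |

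Profile D is the firm result. The register confirms HF, not preserved EF, so the screen leaves D in. D and F can have the same EF, yet one is admitted and the other is not, purely on whether diastolic dysfunction was recorded.

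Profile E is mostly closed. Patients invited from the register already carry an HF label. The register step is not repeated for clinic-visit approaches and is not described for secondary care centres, so E remains open there on the wording only.

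Size. Section 6.0 plans 3 to 4 practices with registers of 50 to 100 patients for the initial sample:

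- Register patients reviewed: 3 × 50 = 150 to 4 × 100 = 400.
- HFpEF or probable HFpEF at 40%: 60 to 160.
- Not so identified: 100% − 40% = 60%, that is 90 to 240.

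The last line bounds the register group that the protocol does not count as HFpEF. It is not an estimate of profile D. The protocol does not say how many of these patients have recorded diastolic dysfunction, how many have a recorded EF, or how many would accept, so the number who entered as D cannot be calculated.

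Under the change set out in the fix, D and E become ineligible on the wording, A, B and C stay eligible, and F stays out.

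**The case against.** The strongest reply is that the breadth is deliberate. Section 2.1 says HFpEF is hard to diagnose and often missed in primary care, and section 6.0 sizes recruitment on probable as well as definite HFpEF. On an HF register, diastolic dysfunction is a sensible marker for probable HFpEF when no EF is reported. This stands for profile C, and any change should keep those patients. It does not cover profile D, where an EF is on record and is below 50%.

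A reader might infer that the study admits anyone with diastolic dysfunction and no heart failure. The protocol does not support that. The criteria are applied to the HF register, section 13.0 says the same procedures are used at all sites, and the section 6.0 phrase about referral most naturally describes practice patients who have been referred, not a separate entry route. What remains is silence about the register step for clinic visits and secondary care centres.

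A reader might also infer that every conclusion is compromised. That goes too far. The amendment's questions in the synopsis cover both HF and HFpEF, and the provider and commissioner interviews, about half of those planned, are initially analysed separately. There is no effect estimate to bias, and section 2.1 itself expects self-management challenges to be similar in the two types of HF, which limits the harm.

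Finally, section 14.0 says the original research has concluded, so new criteria cannot alter who was enrolled. That is correct, and it moves most of the remedy to analysis and reporting.

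**Conclusion.** The inconsistency is real but narrow. Section 7.0 accepts diastolic dysfunction without the preserved EF that its other route demands, no recruitment step makes this good, and the sample is nonetheless described as HFpEF. The missing HF diagnosis is a lesser gap, largely filled by the register screen.

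The size is unknown. The protocol shows that reduced-EF patients could enter, not that any did, and any percentage put on it would be a guess. The conclusion assumes that sites applied section 7.0 as written; a site that informally passed over patients with a known EF below 50% would have no such cases. The consequence is for whether themes can be attributed to HFpEF patients. It does not invalidate the interviews.

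**What to change.** Criteria: amend route 1 so that entry on diastolic dysfunction requires an HF diagnosis and no recorded EF below 50%. This matches the stated population and keeps probable HFpEF with no reported EF. State that the HF diagnosis is also required for clinic-visit approaches and secondary care centres.

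Patients already interviewed: where records allow, assign each to one class, with a recorded EF below 50% taking precedence over any label:

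1. labelled HFpEF;
2. HF with normal EF or EF of at least 50%;
3. diastolic dysfunction only;
4. EF below 50%.

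Report the counts, including those who cannot be classified. Enter the class as a case attribute in the framework charts, and check that themes reported as HFpEF still hold without classes 3 and 4.

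Recall study: flag the class only and exclude nobody. Its questions cover HF and HFpEF, and its inclusion criterion in section 14.0 is ongoing consent to contact.

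Cost: a short amendment, a record check and one more attribute in the existing matrix. The protocol does not describe a screening record showing which route each patient met, so some will remain unclassifiable, and the core HFpEF set will be somewhat smaller.

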8.0 Exclusion Criteria Patients

- Cognitive impairment,
- Non-English speaking
- Receiving end of life care or other life-threatening condition

9.0 Healthcare Provider Sample

There are no inclusion/exclusion criteria for providers. Approximately 50 GPs and practice nurses from practices in the 3 named regions in England, HF specialist nurses, cardiologists, commissioners and others involved in care. We will recruit from urban and rural practices starting in Cambridgeshire and Peterborough then including the same additional sites as for the patient sample.

10.0 Data collection

Patients and providers will be recruited through practices and networks, and invited for interview. Interviews will be conducted via telephone or at a place of person's choosing, audio-recorded with permission and transcribed verbatim. At times the patients' carers may wish to provide information and contribute to the interview. When this happens, with the carer's written consent, we will note their comments and include these in the study.

